## **3.2 SPECIFIC TECHNIQUES USED IN STUDY**

**Ambulatory ECG monitoring:** Participants will be fitted with various ECG monitoring devices to capture prolonged ECG recordings. These will include commercially used Holter monitors up to 12-leads, research grade CE-marked cardiac monitoring devices and wearable ECGs which can be applied for days to weeks at a time to capture long term rhythm recordings.

**Ultra High Frequency ECG:** Our centre is a pioneer in using Ultra-High Frequency ECG (UHF-ECG) to detect, isolate and amplify high frequency components that are filtered out in conventional ECGs. These frequencies (1-2kHz) do not travel far: each chest lead measures only activation of its nearest ventricular wall. We will perform UHF-ECG recordings in our participants to better characterise changes in QRS morphology and activation for diagnosis and risk stratification of arrhythmia syndromes. The UHF-ECG machine is CE-marked.

## **3.3 METHODOLOGY**

### **Study A: Brugada ECG AI development**

The research team will collate at least 3000 ECGs, representing the 3 different categories previously mentioned. All ECGs will be either digital or converted to a digital format using in-house developed software. ECGs will subsequently be processed to enable direct extraction of the ECG complexes from the recordings. The resulting ECG data will be segmented to enable labelling by experts in Brugada ECG analysis.

The anonymous ECG data will be reviewed and annotated by experts. Each ECG will be labelled by 5 individual experts from a larger pool of experts, who will collectively share the task of ECG labelling for our entire training set. Experts will be comprised from the ICC specialists at Imperial College Healthcare NHS Trust, as well as our research collaborators within the UK and internationally. The categorisation of each case will be determined by expert majority agreement.

The labelled ECG data will be divided into the training set (75% of ECG data) and a separate hold-out validation set (25% of ECG data). The training set will be used to train separate neural networks (Appendix 2). Once the neural networks have been developed, they will be tested for their accuracy against a hold-out validation dataset.

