## 3. STUDY DESIGN

### 3.1 RECRUITMENT

#### Brugada ECG AI training

We will collate anonymised Brugada ECG data from UK and international centres. We will collaborate with site-specific representatives to coordinate secure ECG data transmission and acquisition. All ECG data will be anonymised at the point of collection. Consent will not be sought as only anonymised ECGs will be obtained. There will be no access to patient-identifiable data from the research team and all data will be fully anonymised prior to transfer. These ECGs will be acquired from pre-existing hospital digital infrastructure, namely the electronic health record or ECG data management system. Data will be transmitted securely through trusted secure data transfer systems where available. Where this option is not available, ECG data will be physically retrieved via a researcher visiting the centre and copying anonymised data onto an encrypted hard drive.

We will acquire digital ECG recordings as well as scanned paper ECGs of patients with established Brugada syndrome. Paper ECGs will be scanned and imported onto local secure storage. We will also gather anonymised ECG data from Imperial College Healthcare NHS Trust patients. We aim to acquire around 3000 patient ECGs in total for AI training. Where available, corresponding clinical data will also be collected alongside participants' ECGs, including results of any relevant genetic testing and other investigations including ajmaline provocation testing.

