## **7. STATISTICS AND DATA ANALYSIS**

We expect to have access to over 3000 patients' worth of ECG data to train and validate our neural networks, comprising a similar proportion of Brugada and non-Brugada ECGs. Our group has published extensively regarding applications of AI to ECG data (13–17) and includes experienced, independently-funded clinician scientists and engineers with expertise in machine learning. They will guide me in developing neural networks for ECG classification tasks and signal processing. As we will be employing a very similar methodology to our previous successful ECG AI projects in this experiment, we are confident that this quantity of ECG data will be sufficient to develop highly accurate neural networks.

The accuracy of the prolonged duration ambulatory ECG recordings will be calculated using a binomial distribution. Assuming an actual accuracy of 95% and a target accuracy of >85% for ECG analysis discriminating between healthy normal participants and manifest Brugada patients, 90 patients will provide greater than 80% power in demonstrating that the measured accuracy is significantly greater than 85% at the two-tailed 5% significance level. To achieve 90 patients with some loss to follow up, I will recruit 50 healthy volunteers and 50 manifest Brugada patients.

McNemar's test will be used for paired analysis of 24-hour 12 lead Holter and prolonged ambulatory ECG recordings in the concealed arrhythmia patient set. Historical data report 20 to 34% sensitivity for 24-hour Holter for detection of the Brugada ECG pattern in patients with concealed Brugada syndrome (5,6). Assuming 25% sensitivity for 24-hour Holter and 60% for prolonged ambulatory ECG recordings beyond 24 hours, with the prolonged ambulatory ECG recordings being able to identify 80% of 24-hour Holter-identified cases, 35 patients would be needed to provide 90% power at the 5% significance level. I will recruit 50 patients.

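### The protocol does not make the patient the unit of the 75/25 split, and full anonymisation with no stated grouping code may rule out a patient-level split later

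*Protocol*

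**What the plan says.** **Order of steps.** Protocol section 3.3, Study A, first prepares the recordings: "ECGs will subsequently be processed to enable direct extraction of the ECG complexes from the recordings". Then: "The resulting ECG data will be segmented to enable labelling by experts in Brugada ECG analysis". Labelling is per ECG: "Each ECG will be labelled by 5 individual experts from a larger pool of experts". Only after that comes the division: "The labelled ECG data will be divided into the training set (75% of ECG data) and a separate hold-out validation set". The hold-out part is the remaining 25%, again expressed as a share of ECG data. The finished networks are tested for accuracy on it.

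**Size of the dataset.** It is counted in different units. Section 3.3 counts recordings: "The research team will collate at least 3000 ECGs, representing the 3 different categories previously mentioned". Section 7 counts patients: "We expect to have access to over 3000 patients' worth of ECG data to train and validate our neural networks". Section 3.1 speaks of about 3000 patient ECGs. No section gives the number of ECGs per patient or limits it to one.

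**Linkage.** Section 3.1 states: "There will be no access to patient-identifiable data from the research team and all data will be fully anonymised prior to transfer". Section 4.5, Study A, repeats this. Neither mentions a code that would show which ECGs belong to the same patient.

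**Use of the result.** Section 3.4 lists five primary outcome bullets. Three of them are the 12-lead sensitivity, specificity and AUC of networks 1 and 2, network 3, and network 4. The other two are yields of ambulatory monitoring.

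**The concern.** A hold-out set gives an honest estimate of accuracy in new patients only if its patients are new to the network. If another ECG of the same patient was in training, the network can score well by recognising that patient's waveform rather than the disease pattern.

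The risk is greatest for networks 3 and 4. Under Appendix 2 their labels (confirmed Brugada syndrome with a phenotype-negative ECG, and SCN5a status) belong to the patient, so every ECG of that patient carries the same answer. It is weaker for networks 1 and 2, which are trained on the expert reading of the ECG and on a measured angle.

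Repeat ECGs are plausible, though not stated. Section 3.1 draws recordings from health records, ECG management systems and scanned paper at several centres. Section 1.1 describes the Brugada pattern as coming and going, so one patient could supply both positive and negative tracings.

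The point should not wait for an analysis plan. A later plan can prescribe a split by patient, but the team can carry it out only if the ECGs can still be grouped. That is decided before the data leave each site.

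**Working it through.** The protocol states no leakage figure and no sample-size calculation for Study A, so there is no figure to reproduce. The only arithmetic it implies is the size of the two sets.

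**Inputs from the protocol**
- Dataset: 3000 ECGs (section 3.3).
- Split: 75% and 25% (section 3.3), giving 0.75 × 3000 = 2250 for training and 0.25 × 3000 = 750 held out.

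**Assumptions (not in the protocol)**
- Division at random by whole ECG.
- *m* ECGs per patient, or a fraction *q* of patients with two ECGs and the rest with one.

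**Step 1: every patient has *m* ECGs.** A hold-out ECG has at least one same-patient ECG in training with probability 1 − 0.25^(*m*−1).

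| *m* | Calculation | Share of hold-out ECGs affected |
|---|---|---|
| 1 | 1 − 0.25⁰ | 0% |
| 2 | 1 − 0.25 | 75% |
| 3 | 1 − 0.0625 | 93.75% |
| 5 | 1 − 0.0039 | 99.6% |

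**Step 2: only some patients have two ECGs.** The share of ECGs that come from two-ECG patients is 2*q*/(1+*q*). Each of these has its partner in training with probability 0.75.
- *q* = 10%: (0.20/1.10) × 0.75 = 13.6%, about 102 of 750 hold-out ECGs.
- *q* = 20%: (0.40/1.20) × 0.75 = 25%, about 188 of 750.
- *q* = 100%: 1 × 0.75 = 75%, about 563 of 750.

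**Step 3: split by patient.** The share is 0% for every *m* and *q*.

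**Step 4: what this does to accuracy.** The shares above are not a bias. They only limit it under further assumptions. Take a true accuracy of 85% (an illustrative value) and suppose leakage corrected every error on the affected ECGs and changed nothing elsewhere. The inflation would be the affected share × 15 percentage points:
- 0.136 × 15 = 2.0 points at *q* = 10%;
- 0.25 × 15 = 3.75 points at *q* = 20%;
- 0.75 × 15 = 11.25 points at *q* = 100%.

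The real effect would lie between zero and such a ceiling. The protocol gives nothing with which to place it.

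**The case against.** The strongest reply is that the text leaves the unit of the split open and does not choose a wrong one. Several parts of it stand.

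- **Splitting by complex.** Because segmentation precedes the division, a reader might infer that complexes from one recording are spread over both sets. The protocol does not say so. Segmentation is there to enable labelling, each ECG is labelled as a whole, and the hold-out set is called separate.
- **Repeat ECGs.** About 3000 ECGs and over 3000 patients can be read as roughly one ECG per patient. If that is exact and whole ECGs are split, leakage is zero. It would be wrong to say that the protocol plans repeat ECGs.
- **Loss of linkage.** A reader might infer that grouping will certainly be impossible. A bar on identifiable data does not forbid a meaningless code. Section 3.1 has clinical results collected alongside the ECGs where available, and section 8.3 speaks of pseudonymous analysis, though perhaps mainly for recruited participants. Linkage may be lost; it is not shown to be.
- **Other tests.** Study B applies the Brugada algorithms to new recordings from recruited participants. That is a further check, but on ambulatory recordings. It does not replace the stated hold-out test of the 12-lead outcomes.
- **Interval width.** The protocol states no interval method for the hold-out results, so nothing can be held against it there.

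It can also be said that partition details belong in an analysis plan. For the wording of the split alone that would be fair. It does not answer the anonymisation step, which takes effect earlier and which such a plan may be unable to undo.

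**Conclusion.** The point holds in a limited form. Followed literally, the protocol permits one patient's ECGs to fall in both sets, and it does not secure the means to prevent this. The share of hold-out ECGs affected runs from 0% (one ECG per patient, split by whole ECG) through about 14% and 25% (10% and 20% of patients with two ECGs) to 75% (all with two). These figures rest on assumed ECGs per patient and a random split by ECG.

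Any resulting bias would be upwards and would touch the 12-lead accuracy of all four networks, most of all networks 3 and 4. The two ambulatory-yield outcomes are not estimated on the hold-out set. The documents do not support a claim that the results will be inflated, or by how much. Confidence is medium, because the dataset may turn out to hold one ECG per patient.

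**What to change.** - **Section 3.3:** state that the 75/25 division is by patient, with all ECGs and all segments of one patient in the same set.
- **Section 3.1 (and section 4.5, Study A, to match):** have each site attach a meaningless per-patient code to its ECGs before anonymised transfer, so that repeats can be grouped without identifying anyone. Alternatively, state that only one ECG per patient is accepted.

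The cost is two sentences in the protocol and a small task for sites; no extra patients or expert readings are needed under the coding option. Reported accuracy may be slightly lower than under a split by ECG. The one-ECG option needs no code but discards any repeat recordings. The change has to be made before sites transfer data.

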### Study B: Remote arrhythmia diagnostics

In this study, we will undertake validation studies to assess the robustness, accuracy and applicability of the aforementioned AI algorithms (i.e. neural networks) on ECG recordings from several different ambulatory monitoring modalities. This protocol will encompass participants recruited in Groups A-C.

Commented [KS1]: Added for clarity

### Protocol

Participants will undergo the consent process and testing during a single research visit. The steps will include the following:

- Participants will be counselled regarding the research study and written informed consent will be obtained.
- All participants will undergo a 12-lead ECG and ultra-high-frequency ECG recording.
- Group A participants will additionally undergo an echocardiogram to ensure that they have a structurally and electrically normal heart.
- All participants will undergo testing with different ambulatory ECG modalities, depending on availability and resources. This will include Holter monitoring up to 12 leads, wearable cardiac monitoring devices (namely the Boston Scientific BodyGuardian MINI) and other wearable ECG technologies. These devices will be fitted by a member of the research team.
- Participants will be instructed how to maintain continuous ambulatory ECG recording via their device as far as possible, including during day-to-day life and including during sleep. Provisions of additional adhesive patches and devices may be required to facilitate long term monitoring up to 3 months.
- Participants will be provided with a digital symptom and activity diary via email to record their daily activity diary, the occurrence of any arrhythmia-related symptoms and gather real-time feedback on tolerability of their monitoring device. In patients who do not have an email, a paper symptom/activity diary will be provided.
- Data will be remotely uploaded onto the cloud via secure digital infrastructure or housed securely on the cardiac monitoring device.
- Participants will be provided with pre-paid parcels with courier collection for retrieval of the ambulatory ECG devices and wearable ECGs at the end of the 3 month study period.

### Application of ECG AI to ECG recordings

ECG recordings will be downloaded onto local storage. The digital ECGs will be processed and denoised using specialized algorithms developed by the research team. The previously developed ECG AI algorithms for Brugada syndrome will subsequently be applied to the cleaned ECG recordings for all patient groups.

We will establish the sensitivity for the Brugada classification algorithms on recordings from patients with manifest Brugada syndrome (Group C) and their specificity using the recordings from the healthy volunteers (Group A). The algorithms will also be applied to

patients with concealed arrhythmia syndromes (Group B) to determine the diagnostic yield of different ambulatory ECG recording modalities for different time durations. We will apply both the in-house developed Brugada ECG AI algorithms as well as existing ECG AI algorithms developed by external academic or industry collaborators, to investigate for underlying concealed arrhythmias.

**Commented [BK2]:** From this description I think this should be a Pre-clinical device development or performance testing medical device study (no MHRA review required)

**Commented [KS3R2]:** I have amended project filter q2 on IRAS to reflect

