#### Primary Outcome Measures

- Sensitivity, specificity and AUC value for neural networks 1 and 2 to detect the Brugada ECG pattern in 12-lead ECGs.

- Yield of extended duration ambulatory ECG monitoring to detect the Brugada ECG pattern in patients with concealed Brugada syndrome, using neural networks 1 and 2.
- Sensitivity, specificity and AUC value for neural network 3 to diagnose concealed Brugada syndrome from 12-lead ECGs
- Sensitivity, specificity and AUC value for neural network 4 to diagnose an SCN5a mutation from 12-lead ECGs.
- Yield of extended duration ambulatory ECG monitoring to detect the Brugada ECG pattern (neural networks 1 and 2) and LQTS manifestation in patients with idiopathic VF.

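### The concealed-Brugada network (NN3) has no specified prospective accuracy estimate in concealed Brugada patients; only the retrospective hold-out tests it

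*Protocol*

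**What the plan says.** The primary outcomes (Protocol 3.4) include "Sensitivity, specificity and AUC value for neural network 3 to diagnose concealed Brugada syndrome from 12-lead ECGs". Appendix 2 defines what NN3 is for: it learns from ECGs that lack the Brugada pattern but come from clinically confirmed Brugada patients, set against non-Brugada ECGs.

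The networks are tested in two places.

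- **Study A (3.3), retrospective.** The labelled pool is split 75/25, and "Once the neural networks have been developed, they will be tested for their accuracy against a hold-out validation dataset".
- **Study B (3.3), prospective.** The networks are to be validated "on ECG recordings from several different ambulatory monitoring modalities". Under Application of ECG AI to ECG recordings, "The previously developed ECG AI algorithms for Brugada syndrome will subsequently be applied to the cleaned ECG recordings for all patient groups". Sensitivity is then assigned: "We will establish the sensitivity for the Brugada classification algorithms on recordings from patients with manifest Brugada syndrome (Group C"). Specificity is to come from Group A, the healthy volunteers. Group B is used "to determine the diagnostic yield of different ambulatory ECG recording modalities for different time durations".

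In 3.4 the ambulatory yield in concealed Brugada is to be obtained with NN1 and NN2, and the same two networks are named for the Brugada pattern in idiopathic VF. The visit schedule for Study B states: "All participants will undergo a 12-lead ECG and ultra-high-frequency ECG recording". Section 6 confirms that the 12-lead ECG is collected at the index visit.

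**The concern.** The primary objective is to unmask concealed disease, and NN3 is the network built to recognise concealed Brugada from a single 12-lead ECG. Aim 2 in the Study Summary and the opening of Study B speak of prospective validation of the algorithms without leaving NN3 out. Yet the accuracy measures named for the prospective stage do not reach NN3 in its target patients. Sensitivity comes from people whose ECG is already abnormal, and the concealed group has a yield outcome assigned to other networks.

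If the text is followed, NN3's primary outcome rests on a split of the same pool that trained it. Such a split shares the training data's sources, labelling and digitisation, so it cannot show how NN3 behaves in newly recruited patients. The index 12-lead ECGs that could show this are collected anyway.

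**Working it through.** **1. What each source supplies for NN3**

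| Source | Patients | Recording | Accuracy measure named | Reaches NN3 in concealed Brugada? |
|---|---|---|---|---|
| Study A hold-out | Retrospective pool, all categories | 12-lead | Accuracy of the networks | Yes, internal only |
| Study B, Group C | Manifest Brugada | Ambulatory | Sensitivity | No |
| Study B, Group A | Healthy volunteers | Ambulatory | Specificity | Supplies controls only |
| Study B, Group B | Concealed syndromes | Ambulatory | Yield, NN1 and NN2 | Not for NN3 |
| Index visit | All participants | 12-lead | None stated | Could, but no analysis named |

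The hold-out is 0.25 × 3000 = 750 ECGs. The Protocol does not say how many come from concealed Brugada.

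**2. The plan's own sample-size figures (section 7)**

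These reproduce, and none concerns NN3.

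- *Healthy against manifest Brugada.* Exact binomial with n = 90, null 0.85, alternative 0.95 and upper tail 0.025: reject at 84 or more correct. The one-sided error is 0.013 and power is 83.6%, which agrees with the stated figure of over 80%.
- *Concealed Brugada, McNemar.* The discordant probabilities are 0.60 − 0.80 × 0.25 = 0.40 and 0.25 − 0.20 = 0.05, so p_d = 0.45 and d = 0.35. Then n = (1.96√0.45 + 1.2816√(0.45 − 0.35²))² / 0.35² = 34.2, rounded up to 35 as stated. This compares two recording durations, not a network with a reference diagnosis.
- *Idiopathic VF.* 1 − 0.96^50 = 87.0%, as stated.

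**3. What the index ECGs would give**

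The Protocol states no expected NN3 accuracy, so the observed values below are assumptions. The interval for sensitivity is Clopper-Pearson: lower limit = Beta(0.025; x, n − x + 1), upper limit = Beta(0.975; x + 1, n − x).

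| Concealed Brugada patients | Observed | Exact 95% CI |
|---|---|---|
| 50 | 30/50 = 60% | 45% to 74% |
| 50 | 40/50 = 80% | 66% to 90% |
| 50 | 45/50 = 90% | 78% to 97% |
| 35 | 28/35 = 80% | 63% to 92% |
| 25 | 20/25 = 80% | 59% to 93% |

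For AUC against 50 healthy volunteers, the Hanley-McNeil variance is [A(1 − A) + (n − 1)(Q₁ − A²) + (m − 1)(Q₂ − A²)] / (nm), with Q₁ = A/(2 − A), Q₂ = 2A²/(1 + A), n cases and m controls. With n = m = 50 and A = 0.80, the standard error is 0.0445 and the 95% half-width is 1.96 × 0.0445 = 0.087. At A = 0.70 and 0.90 the half-widths are 0.102 and 0.063. With 25 cases they are 0.131, 0.115 and 0.085 at A = 0.70, 0.80 and 0.90.

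**4. Why a range of patient numbers**

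Section 7 plans 50 + 50 + 50 + 50 + 100 = 300 participants, but 3.1 recruits 200 in roughly equal groups. That leaves about 200/3 ≈ 67 in Group B, which cannot hold 50 concealed Brugada plus 50 idiopathic VF patients. The range of 25 to 50 concealed Brugada cases is an assumption made for that reason.

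**The case against.** The case against is substantial, and several stronger readings fail on it.

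- *A reader might infer that NN3 is never validated in concealed Brugada.* The text does not support that. The Study A hold-out tests the networks, and Appendix 2 builds NN3 from the right kind of ECG. The hold-out can therefore supply the primary outcome, which 3.4 does not describe as prospective.
- *A reader might infer that the Protocol measures NN3's sensitivity in the wrong patients.* The sensitivity sentence speaks of classification algorithms. In Appendix 2 only NN1 and NN2 are titled as classifying the Brugada pattern, and manifest Brugada is the right group for them. On that reading the sentence says nothing about NN3.
- *A reader might infer that NN3 is barred from Group B, or that no network may be run on the index ECG.* Neither follows. The algorithms are applied to all groups, and the word recordings could include the index ECG, although Study B is framed around ambulatory devices.
- *A reader might infer a breach of Aim 2.* That aim concerns participants wearing ambulatory devices and does not promise a prospective resting 12-lead test.
- *Detail of this kind often sits in an SAP, which is not shown.*

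What remains is narrower. On either reading of the sensitivity sentence, no prospective sensitivity, specificity or AUC is named for NN3 in concealed Brugada. A positive rate in known cases would act as a sensitivity, but 3.4 assigns that yield to NN1 and NN2. The Protocol itself fixes these populations and networks, so an SAP that followed it literally would carry the gap forward.

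**Conclusion.** The point holds in limited form. NN3 has an internal, retrospective test and no specified prospective one in its target patients. No stated number is wrong, and no two statements flatly contradict each other. The loss is an estimate that the study could have at almost no cost.

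Precision would be moderate: at an observed 80%, the interval is 66% to 90% with 50 patients and 59% to 93% with 25. These figures assume that observed sensitivity, one index ECG per patient, and a clinical diagnosis that is accepted as the reference.

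Independence from training cannot be taken for granted. Study A draws anonymised ECGs from the host Trust, where prospective patients are also identified, so some participants may already have contributed ECGs to NN3's training data.

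**What to change.** In 3.3 (Application of ECG AI to ECG recordings) and 3.4:

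1. State that the Group C sensitivity rule applies to NN1 and NN2.
2. Run NN3 once on the index 12-lead ECG of every participant, with its weights and threshold locked after Study A.
3. Report NN3 sensitivity in concealed Brugada (Group B), specificity in healthy volunteers (Group A) and AUC for that contrast, each with a 95% confidence interval. Use the clinical diagnosis as reference, and set the results beside the hold-out result.
4. Report NN3 positives in idiopathic VF separately and do not count them as false positives. Section 7 expects 3–4% of these patients eventually to be diagnosed with Brugada, and finding them is a study goal.
5. State the number of concealed Brugada patients expected once the 200 and 300 totals are reconciled, with the resulting precision.
6. Record possible overlap between prospective participants and anonymised training ECGs as a limitation.

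The cost is a few lines of text and one extra inference run, with no new patients, visits or recordings.
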